9. CORRELATIVE STUDIES

9.1 Blood Samples

9.1.1 Collection

Approximately 15 mL (3 tubes) of blood will be collected at each time point (a standard 5 mL tube for lipid panel and Hba1c, one 10 mL red/gray research tubes). An additional 8 mL will be collected at the initial blood draw to include a 5mL red top tube for pregnancy test and 3 mL purple EDTA tube are collected for research once only. If blood samples are missed or unable to be obtained at any time point, this will not be considered a deviation and will not affect participant enrollment or continuation on the study. We will test glucose, insulin, lipid profiles (total cholesterol, HDL, LDL, and triglycerides), leptin and adiponectin, several fasting biomarkers, and various genotypes (e.g. MnSOD). The samples will be processed by either the central lab or local laboratories (See Lab Manual). In the event that blood cannot be collected, the subject may still take part in the other portions of the study.

	Baseline	2 months	6 months
Standard 5 mL gold tube (lipid panel, Hba1c)	X	X	X

Pregnancy test 5 mL red tube (if indicated)	X		
Purple 3 mL tube	X		
Red/gray 10 mL tube	X	X	X

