6.2 Exclusion criteria

- 6.2.1 Serious/uncontrolled medical condition at the discretion of the Protocol Chair/designee likely to hinder accurate measurement of weight or any condition for which weight loss is contraindicated or would affect adipokine and inflammatory markers (e.g. active malignancy, end stage renal disease on dialysis, cirrhosis, autoimmune disease, adrenal disease, uncontrolled hypertension, seizure disorder, and history of bariatric surgery)
- 6.2.2 Pregnant or nursing within past 6 months, or plans to become pregnant in the next year

- 6.2.3 Currently enrolled or planning to enroll in a weight loss program (e.g. Weight Watchers, Jenny Craig, Nutrisystem and Medifast) or to take a chronic weight loss medication.
- 6.2.4 Diabetes on insulin or sulfonylureas within the past 3 months
- 6.2.5 Unstable psychiatric disorder or bulimia/anorexia nervosa
- 6.2.6 Alcohol, nicotine or substance abuse; or undergoing abrupt discontinuation of alcohol, benzodiazepine, barbiturate or anti-epileptic drug
- 6.2.7 Use of the following medications are excluded:
 - Tamoxifen
 - MAO inhibitors (must be >14 days from discontinuation)
 - Thyroid medication use unless on stable doses for at least the past 3 months
 - Buproprion containing products or opiate agonists (must be >14 days from discontinuation)
 - Medications that cause weight loss (e.g., lorcaserin, phentermine, orlistat, Qsymia, Contrave) within the past 3 months
 - Medications that are likely to cause weight gain or prevent weight loss (e.g., corticosteroids, lithium, olanzapine, risperidone, clozapine, oral contraceptive pills, hormone replacement therapy) within the past 3 months. NOTE: An exception to this is that SSRI's and SNRI's are allowed if participant has been on stable doses for at least 3 months (if discontinued, a washout of 2 weeks from prior SSRI/SNRI use is required).
 - Medications that may affect adipokine or inflammatory markers (e.g., metformin, glitazones, steroids, ACE inhibitors, beta blockers and statins) unless on stable doses ≥3 months prior to registration (if discontinued, a washout of 2 weeks from prior use is required). Concurrent NSAIDs are allowed if use is limited to <3 times per week; chronic NSAIDs are permitted on study only if use has been ≥3 times per week for at least 3 months prior to registration and is expected to continue.

NOTE: No medication should be discontinued without guidance of the prescribing provider.

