7.3.2 Baseline Visit

The Baseline Visit is in-person and should ideally occur within 8 weeks of the screening visit; with baseline questionnaires completed ≤8 weeks prior.

- Written informed consent
- Physical measurements (weight and height) and BMI calculations
- Vital signs (temperature, blood pressure, heart rate, breathing rate, oxygen level)
- Complete medical history and overall general health (performance status)
- If a documented physical exam is not performed within 3 months, this will be performed at or after baseline visit (but before initiation of the behavioral intervention)
- Meet with weight-loss coach
- Receive Fitbit device for monitoring physical activity (participants will wear this on their non-dominant hand for a minimum of 4 of 7 days with 10 hours per day)
- Receive weight scale
- Check heart rate and blood pressure
- Confirm current medications and medication history
- Blood sample (Pregnancy test for < 60 years of age and not taking medication designed to suppress ovarian function. Will advise contraception for these women.)
- Fecal sample
- Orientation to Fitbit website or smartphone platform by coordinator or coach
- Confirm completion of PROs (or complete in clinic, if needed)

IMPORTANT: Eligibility will be confirmed at the baseline visit. Participants with a BMI of \geq 27 at the screening visit, but with a BMI of \leq 27 at the baseline visit will not have maintained eligibility and will be excluded at present. In addition, if there is \geq 2 kg/m² discrepancy between the screening and baseline visits, the Protocol Chair or designee must be consulted to review the discrepancy; this is to determine that the study endpoints will not be affected by fluctuating/changing weight.

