8. STUDY CALENDAR

D. I	Screening call	Baseline	Follow-Up Visits ##	
Procedure	for eligibility	Visit ##	Week 9	Month 6
Clinical & Physical Assessments:		•	,	,
Consent		X		
Questionnaires		X		
History	X			
Physical exam		$X^{\#}$		
Current medications	X	X		
Performance status		X		
Weight Loss History	X			
Vitals		X	X	X
Up to date screening	X			
mammography within one year	Λ			
BMI Calculation	X*	X	X	X
Anthropomorphic Measurements:				
Height	X*	X		
Weight	X*	X	X	X
Research Correlates:				
Fecal sample		X	X	X
Serum pregnancy test (if age <60)		X		
Lipid panel, Hba1c		X	X	X
Purple research tube		X		
Red/gray research tube		X	X	X
Research Intervention:		•	·	
Patient Reported Outcomes		X	X	X
Provide Fitbit**		X		
Coaching (BWL intervention)***		X	X	X
Provide weight scale		X		

^{*}If greater than 3 months since last documented height and weight in electronic health record, will use patient reported most recent height and weight to determine eligibility based on BMI. However, BMI measured at baseline will serve as first data point.

^{**}Participants will wear the Fitbit on your non-dominant hand for 7 days and a minimum of 4 days with 10 hours per day of wear time.

^{***}Participants will communicate with their coach by phone. The coach will reach out to the participants at the baseline visit, and will provide weekly calls and emails the first 3 months. The last 3 months, participants will receive monthly calls and emails.

[#] Physical exam: may be performed and documented up to 3 months prior to baseline visit by a coinvestigator or provider within the institution. Or physical exam may be performed at or after baseline visit (but before initiation of the behavioral intervention)

Baseline visits should occur within 8 weeks of screening visit. Follow up visits should occur within 8 weeks of assessment date.

NOTE: Additional standard of care tests may be performed at the discretion of the treating investigator as clinically indicated. The schedule should be followed as closely as is realistically possible; however, the schedule may be modified due to problems such as scheduling delays or conflicts (e.g., clinic closure, poor weather conditions, vacations, etc.) with the guidance of the PI/designee, as appropriate, and will not be reportable as a deviation unless the endpoints of the study or subject safety are affected.

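### Section 9.1.1's waiver for missed blood samples makes no exception for the baseline pregnancy test, and so conflicts with the rules that eligibility be confirmed before treatment

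*Combined protocol and SAP*

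**What the plan says.** Section 9.1.1 describes the tubes drawn at each time point and then the baseline extras: "An additional 8 mL will be collected at the initial blood draw to include a 5mL red top tube for pregnancy test", plus a research tube drawn once. The next sentence is the waiver: "If blood samples are missed or unable to be obtained at any time point, this will not be considered a deviation". The sentence then reaches enrolment as well: "this will not be considered a deviation and will not affect participant enrollment or continuation on the study". A later sentence in the same paragraph lets a woman from whom no blood can be drawn take part in the rest of the study. The table below lists the pregnancy tube with the others, at baseline only.

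Other sections bear on the same test:

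- Section 6.2.2 excludes women on these grounds: "Pregnant or nursing within past 6 months, or plans to become pregnant in the next year".
- Section 7.3.2 puts the test at the baseline visit: "Pregnancy test for < 60 years of age and not taking medication designed to suppress ovarian function". It adds that these women will be given contraception advice, and that eligibility is confirmed at this visit.
- Sections 7.2 and 12.1 each say that protocol treatment does not start before eligibility has been confirmed.
- The Section 8 calendar lists "Serum pregnancy test (if age <60)" under Research Correlates, with a mark at baseline only. Its note says that schedule changes "will not be reportable as a deviation unless the endpoints of the study or subject safety are affected".
- Section 7.3 assigns Contrave at week 9 by weight loss alone.

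**The concern.** A waiver for missed blood samples is reasonable for biomarkers and genotyping, where the only loss is a data point. The pregnancy tube is different, because its result bears on a listed exclusion in a trial where more than half of the participants are expected to start a drug. By covering every sample and adding that enrolment is unaffected, 9.1.1 tells a site that this tube may be missed without consequence. Sections 7.2 and 12.1 tell the same site that it may not proceed until eligibility is confirmed.

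At stake is a patient-safety check and the means of seeing that it was missed. If 9.1.1 is followed, an absent test is not a deviation and so need not appear in a deviation log.

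**Working it through.** The point is textual. The plan gives no figure to reproduce, and the conclusion depends on no calculation. The check is whether the sections can all be followed at once when the baseline pregnancy tube is missing.

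1. **Does the waiver reach the pregnancy tube?** It refers to blood samples at any time point, without qualification. The tube is named one sentence earlier as part of the initial blood draw and again in the table. The natural limiting reading, that only research correlates are meant, does not help, because the calendar itself files the pregnancy test under Research Correlates. On the words, the tube is covered.

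2. **What does the waiver then say?** The missing tube is not a deviation and does not affect enrolment or continuation.

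3. **What do the eligibility rules say?** Sections 7.2 and 12.1 make confirmed eligibility a condition of starting treatment, and 6.2.2 is one of the criteria to be confirmed. Neither section says what evidence confirms the pregnancy element. No section makes a negative result an explicit condition of enrolment or of starting Contrave. The general rule therefore does not settle what happens when the tube is missing, whereas 9.1.1 addresses that case directly.

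4. **Is there a later laboratory check?** None is scheduled. The calendar and the 9.1.1 table both mark the test at baseline only, and the week-9 assignment in 7.3 turns on weight loss.

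5. **Does the Section 8 note resolve it?** The note concerns changes to the schedule and keeps them reportable if safety is affected. Section 9.1.1 concerns missed or unobtainable samples and has no such exception. Neither refers to the other.

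6. **Who is meant to be tested?** Section 7.3.2 gives women under 60 who are not on ovarian suppression. The calendar gives women under 60. The 9.1.1 table gives only a when-indicated qualifier. A woman under 60 on ovarian suppression is tested under the calendar but not under 7.3.2, and the 9.1.1 table does not decide between them. It is therefore also unclear in whom a missing tube counts as missing.

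**Size.** Section 13.1 expects 55% of 55 women to be slow responders: 0.55 × 55 = 30.25, or about 30 assigned to Contrave. That is a ceiling under the plan's own assumption, not an estimate. The women concerned are the subset who fall in the tested population and whose baseline tube was missed. The documents give no age distribution, no share on ovarian suppression and no rate of missed draws, so the subset cannot be sized.

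**The case against.** The strongest reply is that 9.1.1 waives a sample and not a criterion. It sits in the correlative-studies section, it is followed by a list of biomarkers and genotypes, and nothing in it claims to supersede Sections 6 or 7. Sections 7.2, 7.3.2 and 12.1 still require eligibility to be confirmed. A complete medical history is taken at baseline, and the questionnaire asks about menstrual periods in the past 12 months. Nursing and planned pregnancy need no blood test. Section 7.3.2 adds contraception advice. On this view a sensible site would never treat the pregnancy tube as optional.

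Most of this stands, and it limits the point. A reader might infer that exclusion 6.2.2 would never be checked. The documents do not support that: only laboratory verification of the pregnancy element can lapse. A reader might also infer that nothing would be written down, but a missing sample that is not a deviation can still be recorded as missing.

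The reply does not remove the conflict. The waiver states in terms that enrolment is unaffected, and of the tubes in 9.1.1 the pregnancy tube is the one tied to a listed exclusion. The calendar's own grouping defeats the argument that only research samples were meant. A site that relies on 9.1.1 is following the text.

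It can also be said that the Section 8 note already protects safety. If it applies, the two sections give different answers on whether the event is a deviation. If it does not, there is no protection from that source. Either way the text needs attention.

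**Conclusion.** The concern holds as a conflict between stated rules. Section 9.1.1, read literally, lets the pregnancy element of 6.2.2 go without laboratory verification in a woman who may later be assigned Contrave, and does not count this as a deviation. Sections 7.2 and 12.1 point the other way, and the Section 8 note contains a safety exception that 9.1.1 lacks. The three descriptions of who is tested are a smaller, related inconsistency. The conclusion rests only on the wording, and how often a tube would be missed is unknown.

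Some further inferences are tempting but not supported:

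- **The primary analysis set could not be verified.** Section 13.4 defines the ITT set as SLOW-BWL women who receive any Contrave. It does not depend on a pregnancy result, so a missing test does not undermine the set.
- **HbA1c raises the same problem.** Section 10.2.3 says what follows from a fall in HbA1c or a change in diabetic medication. It does not make HbA1c a condition of enrolment, so no contradiction with 9.1.1 is shown.
- **A single baseline test contradicts the week-9 drug start.** Section 7.11 lists pregnancy as a reason to stop the intervention but does not promise scheduled retesting. Whether one test is enough is a clinical judgement, not an inconsistency in the documents.

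The point is worth correcting because it concerns patient safety and the correction is small. It does not affect the design's error rates or the primary analysis.

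**What to change.** Reword the waiver in 9.1.1 so that it applies to research correlate samples and states explicitly that it does not extend to a test used to confirm eligibility. The explicit statement is needed: because the calendar lists the pregnancy test under Research Correlates, limiting the waiver to that category alone would leave the gap open. Moving the calendar row out of that group would make the intent plain.

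Reconcile 9.1.1 with 6.2.2, 7.2, 7.3.2, 12.1 and the Section 8 note, so that a site finds one answer on whether a missing pregnancy test bears on eligibility and whether it is reportable. The clinical team should decide how a missing test is handled, and the protocol should then say so in one place.

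State the tested population once and use it in 7.3.2, the calendar and the 9.1.1 table. Which population is right is also for the clinical team.

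The cost is a one-sentence amendment to 9.1.1 plus aligned entries elsewhere. In operation it may mean an occasional repeat draw or an extra logged deviation. Sample size, endpoints and analysis are unchanged.

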9.1.2 Analysis

Biomarkers will be processed and batch analyzed whenever possible to reduce within- and between-batch variability at a designated facility (e.g., the Johns Hopkins Medical laboratories Services).

9.2 Fecal Samples

Participants will provide fecal samples three times during the study and will be provided with the fecal occult blood test (FOBT) to collect the sample at home after a bowel movement. They will ship the fecal sample to the lab of [name] at Johns Hopkins University. Upon arrival at the lab, the specimens will be stored at -80° C and will be processed for microbiome analyses. Analysis targeting the V4 region of the 16S rRNA gene will be performed using an Illumina MiSeq and analyses of the microbiome samples will be performed using the Quantitative Insight into Microbial Ecology (QIIME) suite, V.1.7 and a QIIME wrapper (QWRAP).

9.3 Leftover Samples

Any leftover study blood and stool samples will be stored for future research studies, including predictive biomarker studies. These samples may be released for use in future studies after approval by the Protocol Chair and other regulatory bodies, as appropriate.

9.4 Additional information

The correlative sample collection schedules outlined are based on an ideal subject. The sample schedule should be followed as closely as is realistically possible; however, the schedule may be modified due to problems such as scheduling delays or conflicts (e.g., clinic closure, poor weather conditions, vacations, etc).

10. ADVERSE EVENTS

10.1 General

This study will use the descriptions and grading scales found in the revised National Cancer Institute Common Terminology Criteria for Adverse Events (CTCAE) Version 4.0 for adverse event reporting that can be found at http://ctep.cancer.gov/reporting/ctc.html. Information about all related adverse events, whether volunteered by the subject, discovered by investigator questioning, or detected through physical examination, laboratory test or other means, will be collected, recorded, and followed as appropriate.

It should be noted that only those adverse events believed to be related to the weight loss intervention will be collected and tabulated during the course of the study. The side effects with

the weight loss intervention we might encounter include anxiety and frustration. While this program is not designed to cause radical weight loss, in the unlikely event this were to occur radical weight loss can cause several medical implications including dehydration, malnutrition, electrolyte disturbances, headaches, nausea, and tachycardia. Blood samples for research correlated will require intravenous access which may include discomfort, bruising and, rarely, infection, syncope, or significant bleeding; these will be collected at planned standard of care testing, whenever possible.

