3. HYPOTHESIS

- In SLOW-BWL, adding Contrave at week 9 of a weight loss intervention may augment BWL and allow women to lose \geq 5% of their baseline body weight at 6 months.
- In SLOW-BWL, weight loss of $\geq 5\%$ baseline body weight will be associated with changes in the following from baseline to 2 and 6 months:
 - o reductions in fasting glucose, fasting insulin, total and low-density lipoprotein (LDL) cholesterol, triglycerides, leptin;
 - o increases in high-density lipoprotein (HDL) cholesterol and adiponectin;
 - o altered gut microbiome (decrease in the ratio of bacteroides and firmacutes); and
 - o improved patient reported outcomes (PROs)
 - o increased total lean mass, and decreased % fat mass and visceral fat
- Compared to women who are able to achieve at least 5% weight loss with 2 months of behavioral intervention alone, women who are unable to achieve ≥5% weight loss with behavioral intervention alone may have identifiable baseline characteristics (i.e., cardiometabolic profile, obesity biomarker, microbiome composition or PROs) that may be predictors of whom may benefit from earlier initiation of pharmacotherapy.

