continue at lowered dose. If symptoms persist, dose can be lowered by 50% again. If symptoms are alleviated, patient can continue at lowered dose. However, if symptoms persist, the medication should be discontinued and the patient should continue with BWL alone. Following the prescribing information, Contrave will be discontinued for patients who do not achieve \geq 5% and seen in person once a month to assess compliance and potential side effects.

The weight loss intervention is based on the remote-support arm of the POWER trial that was also used by our team in a previous study in breast cancer survivors^{3,4}. It involves two main components: an online portion that participants access on their computer or phone and a telephone/teleconferencing portion to help monitor progress and deliver the behavioral intervention. All participants will receive the POWER intervention, which will be remote and last 6 months. Participants will be given a physical activity monitor (Fitbit) that encourages increased activity by measuring steps and process variables, such as heart rate and sleep. Participants will use a web-based platform to access learning materials and log their diet and exercise each day. They will also record their weight once weekly through our survey. As participants monitor their own progress, they will receive telephone/teleconferencing calls on a regular schedule by a weight loss coach to help monitor and guide progress utilizing dietary, physical activity and weight information. All contacts will be phone/teleconferencing based and last about 30 minutes. For all participants, contacts will occur weekly during the first 3 months (a baseline visit followed by 12 phone sessions) and monthly for the remaining 3 months (3 phone sessions). At the conclusion of the study after 6 months of behavioral intervention, participants will have an in-person visit.

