10.3 Definitions

• Adverse event (AE): Any undesirable sign, symptom or medical condition occurring after starting therapy even if the event is not considered to be related to the study. An undesirable medical condition can be symptoms (e.g., nausea, chest pain), signs (e.g.,

tachycardia) or the abnormal results of an investigation (e.g., laboratory findings, biopsies).

Medical conditions/diseases present before starting study treatment are only considered adverse events if they worsen after starting study treatment (any procedures specified in the protocol). Adverse events occurring before starting study treatment but after signing the informed consent form will be recorded. Abnormal laboratory values or test results constitute adverse events only if they induce clinical signs or symptoms or require therapy.

Serious adverse event or reaction: Any untoward medical occurrence secondary to therapy that: results in death, is immediately life-threatening, requires inpatient hospitalization or prolongation of existing hospitalization, results in persistent or significant disability / incapacity, or is an important medical event that may jeopardize the subject or may require medical intervention to prevent one of the outcomes listed above.

The definition of serious adverse event (experience) also includes *important medical* event. Medical and scientific judgment should be exercised in deciding whether expedited reporting is appropriate in other situations, such as important medical events that may not be immediately life-threatening or result in death or hospitalization but may jeopardize the patient or may require intervention to prevent one of the other outcomes listed in the definition above. These should also usually be considered serious.

A hospitalization planned before the start of the study agent(s) and/or for a preexisting condition that has not worsened does not constitute a serious adverse event (e.g., elective hospitalization for breast reconstruction of the ipsilateral breast). A hospitalization for a social reason in the absence of an adverse event also does not meet the criteria for a serious adverse event.

- Unexpected adverse event: An adverse event, which varies in nature, intensity or frequency from information on the investigational intervention provided in the Investigator's Brochure, package insert or safety reports. Any adverse event that is not included in the informed consent is considered "unexpected".

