10.4 Relationship

The relationship of all adverse events and serious adverse events to study medication will be assessed by an investigator and assigned as follows:

- Definitely: An adverse event which has a timely relationship to the administration of the investigational drug/agent, follows a known pattern of response, for which no alternative cause is present.
- Probably: An adverse event, which has a timely relationship to the administration of the investigational drug/agent, follows a known pattern of response, but for which a potential alternative cause may be present.

- Possibly: An adverse event, which has a timely relationship to the administration of the investigational drug/agent, follows no known pattern of response, but a potential alternative cause does not exist.
- Unlikely: An adverse event which does not have a timely relationship to the administration of the investigational drug/agent, follows no known pattern of response, does not reappear or worsen after re-administration of the investigational drug/agent (if applicable), and for which there is evidence that it is related to a cause other than the investigational drug/agent.
- Unrelated: An adverse event, for which there is evidence that it is definitely related to a cause other than the investigational drug/agent. In general, there is no timely relationship to the administration of the investigational drug/agent, or if there is a timely relationship, the event does not follow a known pattern of response, and there is an alternative cause

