10.5 Reporting Procedures

10.5.1 General

All adverse events will be captured on the appropriate study-specific case report forms (CRFs) through CRMS and REDCap. The Coordinating Center may also periodically request that deidentified AE logs and deviation logs be submitted via encrypted email, such as for annual continuing review.

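### Section 10.1 collects only adverse events believed related to the weight loss intervention, contradicting 10.5.1 and the pre-treatment recording rule in 10.3; graded records of non-serious events judged unrelated could be absent from the safety summary

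*Combined protocol and SAP*

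**What the plan says.** Section 10.1 (General) limits adverse event data to related events in two places. Its first paragraph describes what will be recorded as "Information about all related adverse events, whether volunteered by the subject, discovered by investigator questioning" and so on. Its second says that "only those adverse events believed to be related to the weight loss intervention will be collected and tabulated during the course of the study".

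Other parts of section 10 read differently:

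- **10.3 (Definitions)** defines an adverse event as one arising once therapy has begun, "even if the event is not considered to be related to the study". It adds: "Adverse events occurring before starting study treatment but after signing the informed consent form will be recorded".
- **10.4 (Relationship)**: "The relationship of all adverse events and serious adverse events to study medication will be assessed by an investigator". The scale runs from Definitely down to Unlikely and Unrelated.
- **10.5.1 (General)**: "All adverse events will be captured on the appropriate study-specific case report forms".
- **10.5.2** sends all serious events to the PI whatever their cause.
- **10.5.3** sends all events to the IRB, subject to institutional standards that the protocol does not reproduce.

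On analysis, 13.2 promises a descriptive summary of safety data across the study. Section 13.4 defines a safety population that covers women on the behavioural programme alone and women who also receive Contrave. Neither says whether the summary covers all adverse events or only related ones.

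**The concern.** Site staff need one rule for what goes on the form. Here they have two that point in opposite directions for the same event. Under 10.1, someone must first judge whether an event is related, and an event judged unrelated is not collected. Under 10.5.1 it is collected and 10.4 then grades its relationship.

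The order matters. This is a single-arm, non-randomised trial, so there is no concurrent control group against which a pattern of events could be checked. If relatedness decides what is recorded, the judgement cannot be re-examined later, because the event is not in the database. If events are recorded first, the judgement can be revisited. Different staff could also follow different sections, and the completed forms would not show which rule was used.

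A second ambiguity adds to this. Section 10.1 judges relatedness to the weight loss intervention and 10.4 judges it to study medication. The protocol does not say whether the first term includes the second.

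**Working it through.** No power, alpha or event rate is involved, so the check sets the rules side by side and applies them to specific kinds of event.

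**1. Non-serious event after the start of treatment, judged unrelated.** Section 10.1: not collected, not tabulated. Section 10.5.1: captured on the case report form. This is a direct contradiction.

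**2. Event after consent but before treatment starts.** Section 10.3: recorded. Section 10.1: recorded only if believed related to an intervention that has not begun, which can hardly apply. This is a second direct contradiction.

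**3. The 10.3 definition and 10.4.** Neither forces collection by itself. A definition says what counts as an adverse event, and 10.4 says how relationship is graded. Both fit 10.5.1 better: if 10.1 were followed, the Unlikely and Unrelated grades of 10.4 would be largely unused for non-serious events.

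**4. Can 10.1 be read as a limit on tables only?** That would reconcile the sections, but the sentence covers collection as well as tabulation, and the paragraph before it also limits recording to related events.

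**5. Serious event judged unrelated.** Section 10.5.2 sends it to the PI whatever the cause. The serious-event definition in 10.3 is tied to therapy, which sits awkwardly with this, but the reporting rule in 10.5.2 is explicit. The gap is therefore confined to non-serious events.

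**6. Event attributed to Contrave and not to the behavioural programme.** The result depends on what the weight loss intervention means.

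- *Suggesting that it excludes the drug:* section 7.3 describes the weight loss intervention thus: "It involves two main components: an online portion that participants access on their computer or phone and a telephone/teleconferencing portion", with no drug component. Section 3 speaks of "adding Contrave at week 9 of a weight loss intervention may augment BWL", so the drug is added to the intervention. The opening of 10.2 refers to the remote-support programme.
- *Suggesting that it includes the drug:* section 7.6.1 describes the goals of the intervention in months 3 to 6 as adding pharmacotherapy. Contrave symptoms (10.2.6) are listed under the risks of the intervention. Section 10.4 grades relationship to study medication. The safety population in 13.4 includes women on Contrave.

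The documents do not settle this. The contradictions in steps 1 and 2 exist on either reading.

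**7. Is the information held elsewhere?** Section 7.3 and Appendix C provide a weekly question on new symptoms for all participants in months 3 to 6, with no relatedness filter, and send entries for evaluation. SLOW-BWL women also list side effects in the drug diary (Appendix G). Detection is therefore likely. No passage says that these entries become adverse event records. What may be missing is the graded record, not all trace of the symptom.

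**8. Scope.** Section 13.1 plans 55 women, 55% of them in SLOW-BWL: 0.55 × 55 = 30.25, about 30 expected to receive Contrave, leaving about 25. The 10.1 rule applies to all 55. No count of lost events can be derived, because the documents give no share of events judged unrelated. The rates in 10.2.6 come from other trials of differing lengths and do not supply that share.

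**The case against.** The best case for the plan is that this is untidy wording with little consequence. Section 11.3 classes the trial as low risk with no investigational drug. Serious events are covered. Symptom entries are stored in REDCap, which 10.5.1 also names as a route for adverse event capture. The safety summary in 13.2 is not restricted to adverse event tables. Collecting only related non-serious events, if clearly stated, could be a deliberate choice.

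Much of this stands, and it limits the consequence: events *could* be absent from the summary, and only as graded records. It does not remove the contradiction. The protocol does not clearly state a related-only policy; it states that policy in 10.1 and the opposite in 10.5.1. A low-risk label does not tell staff which to follow.

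A reader might infer three stronger things that the documents do not support.

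- *That Contrave side effects will go unrecorded.* This needs the narrow reading of weight loss intervention, and 7.6.1, 10.2.6, 10.4 and 13.4 all count against it.
- *That the safety summary will lack these events.* This assumes that every site follows 10.1 over 10.5.1 and that the symptom entries are not used.
- *That the lack of data on these medications with hormonal therapy, noted in section 1, makes the gap worse.* A suspected interaction would normally be judged drug-related and so collected on the broader reading. The same sentence also names tamoxifen, which 6.2.7 excludes.

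**Conclusion.** Wrong as written: the collection rules contradict each other. Section 10.1 cannot be followed together with 10.5.1 or with the pre-treatment recording rule in 10.3, and it fits poorly with 10.4. The consequence is that graded records of non-serious events judged unrelated could be absent from the 13.2 summary. Loss of drug-related events is a possibility only.

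The effect cannot be put as a number. It does not touch the primary endpoint or the reporting of serious events to the PI. The conclusion assumes that no text outside what was available resolves the conflict. A short stretch after 10.5.3 was not available, but the contents list shows no further section there. The change is worth making because the present wording lets a judgement made before recording decide what safety data exist, and correcting it is cheap.

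**What to change.** - Replace the restriction in 10.1 (both sentences) with the rule already present in 10.3 and 10.5.1: record all adverse events from consent onward, in all participants, FAST-BWL and SLOW-BWL alike.
- Assign relatedness afterwards under 10.4, separately for Contrave and for the behavioural programme. The meaning of weight loss intervention then no longer decides what is recorded.
- State that symptoms from the weekly survey (Appendix C) and the drug diary (Appendix G) are reviewed for entry as adverse events.
- State in 13.2 that the safety summary uses all recorded adverse events in the 13.4 safety population, with related events shown as a subset if wanted.

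The cost is wording changes and modest extra adverse event data entry for about 55 women. No visit, sample or sample size changes.
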